#### **12.4 \* Provide a description of the Statistical Analysis Plan (including rationale for number of subjects recruited for the study and the statistical method(s) by which the data will be analyzed)**

Based on previous MHRN research, we presume that 10% of participants assigned to usual care will initiate treatment within 60 days of randomization (after not initiating treatment in the first 30 days after diagnosis) and that only 2% will disenroll from participating health systems (i.e. outcome data not available) within 60 days. A sample size of 200 per group across both sites will afford 90% power (chi-square statistic with 2-sided type 1 error of 5%) to detect an increase from 10% to 22% in those assigned to the outreach intervention. Within any specific racial or ethnic group, the anticipated sample size of approximately 50 per group would afford 80% power to detect an increase from 10% to 33% in those assigned to the outreach intervention. In other words, this pilot study will have adequate power to detect moderate to large increases in treatment initiation and will not have adequate power to examine effects on ultimate clinical outcomes (i.e., HEDIS response and remission rates).

The primary trial outcome will be initiation of formal depression treatment within 60 days of randomization, defined as either at least one filled prescription for any antidepressant medication or attending at least one individual psychotherapy visit. Two secondary outcomes (recording of depression remission or response) will be defined and assessed using NCQA/HEDIS Electronic Clinical Data Systems specifications for depression response and remission. Those specifications identify recorded response (i.e. 50% or greater decrease in PHQ-9 score from baseline) and remission (i.e. any recorded PHQ-9 score of less than 5) among all patients with new diagnoses and baseline PHQ9 scores of 10 or higher. Following HEDIS specifications, failure to record clinical outcome will be considered failure to achieve response or remission.

Descriptive analyses will examine baseline participant characteristics (age, sex, baseline PHQ-9 score, history of prior depression treatment) and examine uptake or acceptance of specific intervention activities, including:

- Proportion of intervention participants reading initial outreach messages
- Proportion responding to initial outreach and completing outreach assessment
- Proportion of those not responding to online messages who respond to subsequent telephone outreach
- Distribution of PHQ-9 responses, perceived need for treatment, and perceived treatment barriers among those completing outreach assessment (by online messaging or telephone).
- Proportion initiating any treatment or specific type of treatment (medication or psychotherapy) according to response to outreach, PHQ-9 score at initial assessment, perceived treatment need at initial assessment, and perceived barriers to treatment at initial outreach.

Sample size permitting, each of these analyses will be stratified by race/ethnicity group.

Analyses of primary outcomes will compare rate of treatment initiation within 60 days (defined above) among all patients originally assigned to the intervention condition to the rate among those assigned to continued usual care, regardless of acceptance of or participation in the outreach intervention (i.e. intent-to-treat analysis). Unadjusted comparisons will use chi-square statistics to compare rates, and adjusted analyses will use logistic regression, adjusting for age group, history of prior depression treatment (medication or psychotherapy), baseline PHQ-9 score, and site. Analyses of secondary outcomes (depression remission and response by HEDIS specifications) will follow the same scheme.

We do not propose any “as treated” or “per protocol” analyses limited to patients who accept or respond to outreach interventions. Because it is not possible to identify usual care patients who would have declined intervention services, any comparison of intervention “accepters” to the full usual care sample would be fundamentally and irreparably biased.

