Provider Survey: Providers will be recruited digitally to complete a brief 10-minute survey (Provider Recruitment Email.doc). We will work with clinical liaisons within each health system to recruit eligible providers. Invitations to providers will either be sent by the Site-PI or a designated clinical partner (e.g., [name] at KPHI). The survey invitation will contain an informational sheet (Provider\_Information\_Sheet.doc) that will be attached to the electronic message and attached as an attachment.

Phase III:

Once a participant is determined to be eligible for the study using the algorithm described in previous sections, the participant will be randomized to either standard care or outreach messaging groups. Participants randomized to standard care will not be contacted by the project team. Follow-up data will be collected (see previous section) regarding treatment initiation and depression remission (follow-up PHQ-9 scores) for 60 days after randomization for standard care participants. Participants randomized to the outreach group will receive either an initial phone call or secure message from the study team. For participants with PHQ-9 score less than 15 and a response <2 to PHQ-9 item 9, initial contact will be by online message. For participants with PHQ-9 score ≥15 or response to item 9 ≥2, initial contact will be by telephone. Up to four outreach attempts will be made per participant. If initial outreach occurs by secure message and it is not read within three days of sending, up to three telephone outreach attempts. Telephone outreach will take two times in one week, and then two weeks following the last attempt.

We propose a waiver of the usual requirement for informed consent to identify potential participants and assign patients to either continued usual care or attempted outreach. We believe that this approach (waiver of consent in such a modified Zelen or randomized encouragement design to evaluate a low-risk outreach intervention) satisfies regulatory requirements and ethical standards for waiver of consent. Use of this approach in similar previous MHRN trials has been vetted with the DHHS Office for Human Research Protections and approved by MHRN health system institutional review boards.

For participants assigned to outreach, the initial outreach message will include abbreviated informed consent information, including (see outreach message consent document):

- Description of the outreach program

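### Recorded response and remission score an unrecorded PHQ-9 as failure; if outreach changes how often PHQ-9s are recorded, these rates can differ between arms with no clinical benefit

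*Combined protocol and SAP*

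**What the plan says.** Section 12.4 sets the secondary outcomes as follows: "Two secondary outcomes (recording of depression remission or response) will be defined and assessed using NCQA/HEDIS Electronic Clinical Data Systems specifications". Response is a recorded fall of at least half from the baseline PHQ-9; remission is any recorded score below 5. Unrecorded outcomes are handled by one rule: "Following HEDIS specifications, failure to record clinical outcome will be considered failure to achieve response or remission".

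The descriptive analyses in 12.4 show that a PHQ-9 is obtained during outreach. They include "Distribution of PHQ-9 responses, perceived need for treatment, and perceived treatment barriers among those completing outreach assessment (by online messaging or telephone", and they break down treatment initiation by "PHQ-9 score at initial assessment, perceived treatment need at initial assessment, and perceived barriers to treatment at initial outreach".

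The control arm has no counterpart. Section 22.1 (Phase III) says: "Participants randomized to standard care will not be contacted by the project team". The Pilot Trial Design part of 12.2 takes outcomes from health system records over the 60 days after assignment.

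The comparison is the intent-to-treat chi-square test and adjusted logistic regression used for the primary outcome: "Analyses of secondary outcomes (depression remission and response by HEDIS specifications) will follow the same scheme". Nothing in the document says whether scores collected by outreach clinicians count, compares PHQ-9 recording between arms, or gives an alternative treatment of unrecorded scores.

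**The concern.** When missing counts as failure, a recorded success needs two things: a score in the record, and a score that meets the threshold. Outreach could change the first without the second, by two routes.

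- **Direct.** The outreach assessment itself yields a PHQ-9 that enters the record and is counted as follow-up.
- **Indirect.** Outreach brings more patients into treatment, and treated patients have more visits at which a PHQ-9 may be recorded. Since any single score below 5 is remission, each further recording is another chance of success.

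The planned logistic regression adjusts for baseline factors and site. It cannot correct a difference in recording that arises after randomisation.

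These are the only clinical outcomes compared between arms, in a pilot meant to inform a full-scale trial. A difference due to recording could be carried into that planning as evidence of benefit.

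**Working it through.** **1. The plan's own power figure.** Inputs from 12.4: 200 per group, 10% versus 22%, two-sided 5%, chi-square. The pooled proportion is 0.16.

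- SE under the null = √(2 × 0.16 × 0.84 / 200) = 0.03666
- SE under the alternative = √((0.10 × 0.90 + 0.22 × 0.78) / 200) = 0.03617
- Power = Φ((0.12 − 1.96 × 0.03666) / 0.03617) = Φ(1.33) = 0.908

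The stated 90% reproduces and is not in dispute. The plan gives no figure for the secondary outcomes.

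**2. Model for recorded success.** Let *r* be the chance that a follow-up PHQ-9 is recorded and *q* the chance of success given a recording. Recorded rate = *r* × *q*. With *q* equal in both arms (no clinical benefit), the expected ratio of recorded rates is simply the ratio of recording rates.

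**3. Assumptions, because the documents give no recording rates.** *q* is 20–40% in both arms; *r* is 20–40% in usual care and 30–60% in outreach, in 10-point steps, keeping only combinations where outreach records more. The chance of p<0.05 comes from exact binomial enumeration of the uncorrected chi-square test, 200 per arm.

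| *q* | *r* usual care | *r* outreach | Recorded rates | Chance of p<0.05 |
|---|---|---|---|---|
| 20% | 30% | 30% | 6% v 6% | 4.7% (equal recording, for reference) |
| 20% | 40% | 50% | 8% v 10% | 10% (lowest) |
| 20% | 30% | 40% | 6% v 8% | 11.7% |
| 30% | 30% | 50% | 9% v 15% | 45.5% |
| 30% | 20% | 40% | 6% v 12% | 55.5% |
| 40% | 20% | 40% | 8% v 16% | 69.9% |
| 40% | 20% | 60% | 8% v 24% | 99.5% (highest) |

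Hand check of 6% v 12% by the formula in step 1: pooled proportion 0.09; SEs 0.02862 and 0.02846; Φ((0.06 − 1.96 × 0.02862) / 0.02846) = Φ(0.14) = 0.555.

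With equal recording the chance returns to about the nominal 5%, so the excess comes from recording alone.

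**4. Indirect route only.** Suppose outreach-collected scores never count. Assume a PHQ-9 is recorded in 90% of patients who start treatment and 25% of those who do not, and take the plan's 10% versus 22% as the initiation rates.

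- Usual care: 0.10 × 0.90 + 0.90 × 0.25 = 31.5% recorded
- Outreach: 0.22 × 0.90 + 0.78 × 0.25 = 39.3% recorded
- *q* = 20%: 6.3% v 7.9% recorded success; chance of p<0.05 about 9%
- *q* = 40%: 12.6% v 15.7% recorded success; chance of p<0.05 about 15%

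**The case against.** A reader might infer that outreach PHQ-9s are charted and feed the outcome, so that recording differs by design. The documents do not establish this. Section 12.4 shows only that these answers will be described. No section says they are entered in the health record or count as follow-up, and 25.2 says Phase III participants are not asked to complete study procedures, which needs reconciling with the assessment in 12.4. The adopted HEDIS specifications may also settle which scores qualify; they are cited, not reproduced.

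The size is open to challenge too. The outreach PHQ-9 is taken at initial assessment, from patients who under 12.2 scored 10 or more around diagnosis, went 30 days without treatment and have no score below 5 since. Giving such early scores the same success rate as a later routine score probably overstates the direct route, above all for remission. Section 12.2 also expects telephone outreach to consist mostly of reminder messages, so a 20-point gain in recording is not anchored in the plan.

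Finally, 12.4 labels the outcomes as recordings, discloses the missing rule and concedes inadequate power for clinical outcomes. For recorded response taken literally, 6% versus 12% is a real difference; the hazard lies in reading it as improvement.

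All of this stands, and it limits certainty and severity. It does not remove the point. The silence on which scores count is itself a gap, the indirect route needs no outreach-collected score, and low power for a true effect is no safeguard against a systematic difference in measurement. Section 12.4 also refers to HEDIS response and remission as ultimate clinical outcomes, which invites the clinical reading.

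**Conclusion.** The concern holds as a possibility that the plan neither rules out nor would reveal. Followed as written, the analysis can show a between-arm difference in recorded response or remission that comes from recording alone.

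The size cannot be fixed from the documents. Under the assumed recording rates, with equal true response and outreach recording above usual care, the chance of p<0.05 is about 10% to 99.5%. By the indirect route alone, on its own assumed rates, it is about 9–15%. Both rest on equal success among those recorded. If outreach did not raise recording, this bias in its favour would not arise.

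A reader might go further and conclude that the trial's main result is compromised. It is not: the primary outcome is a prescription fill or an attended psychotherapy visit, which does not depend on PHQ-9 recording, and its power calculation reproduces. For openly labelled, admittedly underpowered secondary outcomes this is a should-fix.

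**What to change.** In 12.4:

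1. State whether PHQ-9s collected by outreach clinicians, by message or telephone, count as follow-up, and run the HEDIS outcome with and without them. Exclusion alone is not enough: it closes only the direct route, and could work against outreach if clinicians do not repeat a recently taken PHQ-9.
2. Report by arm the proportion with any follow-up PHQ-9 in the 60 days.
3. Keep missing as failure for the HEDIS analysis, and add a sensitivity analysis for unrecorded scores by inverse-probability weighting or multiple imputation, with the missing-at-random assumption stated.
4. Describe the results as recorded rates, not as clinical benefit, when recording differs by arm.

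The cost is SAP wording, a source filter in the extraction code and some added analysis. The intervention and sample size do not change. The drawback is that the model-based results rest on an untestable assumption, with possibly a large share of scores unrecorded (40–80% under the recording rates assumed above), so they should be read as sensitivity checks.

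### The last descriptive bullet of section 12.4 relates treatment initiation to outreach response and assessment findings without requiring these to precede the treatment start

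*Combined protocol and SAP*

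**What the plan says.** Section 12.4 defines the primary outcome as "initiation of formal depression treatment within 60 days of randomization". The event is "either at least one filled prescription for any antidepressant medication or attending at least one individual psychotherapy visit". The clock therefore starts at randomization, whether or not the patient has yet been contacted.

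The last descriptive bullet of the same section then tabulates "Proportion initiating any treatment or specific type of treatment (medication or psychotherapy) according to response to outreach, PHQ-9 score at initial assessment", together with "perceived treatment need at initial assessment, and perceived barriers to treatment at initial outreach". The bullet before it makes clear that PHQ-9, need and barriers come from the outreach assessment, completed online or by telephone. That assessment is necessarily after randomization.

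Section 22.1 (Phase III) gives the contact schedule. Some patients are telephoned first and others get a portal message first. If a message is unread after three days, up to three calls follow. On their spacing the plan says: "Telephone outreach will take two times in one week, and then two weeks following the last attempt". No interval from randomization to the first message is stated. In section 12.2, telephone follow-up is triggered by an unread message, so a patient who has read the message may reply at any later time.

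The eligibility rule on being untreated (section 12.2) covers only the 30 days after diagnosis. Section 12.2 also has clinicians review the chart and track treatment initiation. It does not say how a patient who starts treatment before being assessed is to be handled in the table.

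**The concern.** A table of initiation by a factor is normally read as if the factor came first. Here it need not. A patient who fills a prescription on day 6 and is first reached on day 20 would be tabulated by a PHQ-9 score, perceived need and perceived barriers reported two weeks into treatment. The same patient would count as having initiated among responders, although the response followed the start.

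The opposite error is also possible. Clinicians track initiation, and if they stop calling once a start is seen, the early starter is never assessed and falls among the non-responders because treatment began early.

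The pilot is meant to inform a full-scale trial, and these are the only quantitative tables listed in the plan that link need and barriers to initiation. A gap between rows could reflect the order of events rather than who acts on outreach.

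**Working it through.** **Inputs from section 12.4.** 200 patients per group; 10% starting within 60 days under usual care; 22% under outreach. In the outreach arm that is 0.22 × 200 = 44 starts, of which 0.10 × 200 = 20 correspond to the background rate and 24 are the planned excess.

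**The plan's own figure.** The table has no stated figure. The power statement that supplies the inputs reproduces (pooled chi-square, no continuity correction): z = [0.12√200 − 1.96√(2 × 0.16 × 0.84)] / √(0.10 × 0.90 + 0.22 × 0.78) = (1.697 − 1.016)/0.511 = 1.33, power 90.8% against the stated 90%. Nothing below changes it.

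**Contact window (section 22.1).** Three days' wait, two calls within a week (days 3 to 10), and another call 14 days after the last: 3 + 14 = day 17 at the earliest, 10 + 14 = day 24 at the latest, counted from the message.

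**Assumptions not in the documents.** 50% respond; the message goes out at randomization; first response is uniform over days 0-10 or 0-24; response is unrelated to starting.

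**Misordered patients, even spread of starts.** The chance that a start precedes contact is the mean contact day divided by 60. Patients misordered = 200 × 0.5 × rate × (T/2)/60.

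| Starts that can precede contact | T = 10 | T = 24 |
|---|---|---|
| Background only, 10% | 100 × 0.10 × 5/60 = 0.8 | 100 × 0.10 × 12/60 = 2.0 |
| All planned, 22% | 100 × 0.22 × 5/60 = 1.8 | 100 × 0.22 × 12/60 = 4.4 |

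**The same with a constant start rate.** h = −ln(1 − rate)/60, and the fraction started before contact is π = 1 − (1 − e^(−hT))/(hT). At 22%, h = 0.00414, so π = 0.020 for T = 10 and 0.048 for T = 24, or 2.0 and 4.8 of 100 responders. At 10% it is 0.9 and 2.1. As a share of starters among responders at 22%: 0.0204/0.22 = 9% and 0.048/0.22 = 22%.

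**Effect on a need table with no true link (22%, T = 24).** Starts after assessment are 0.22 − 0.048 = 0.172. Let half of patients report high need, except early starters, of whom a fraction q do.

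- q = 0.9: high need (0.048 × 0.9 + 0.086)/(0.048 × 0.9 + 0.476) = 24.9%; low need (0.0048 + 0.086)/(0.0048 + 0.476) = 18.9%.
- q = 0.25: high need 0.098/0.488 = 20.1%; low need 0.122/0.512 = 23.8%.
- Only later starts among those still untreated: 0.172/0.952 = 18.1% in both rows.

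**Effect on the response table if outreach stops at a start (50% responding, T = 24).** Responders: 0.172/0.952 = 18.1%. Non-responders: (0.5 × 0.22 + 0.024)/(0.5 + 0.024) = 25.6%. Again there is no true link.

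**The case against.** The tables are labelled descriptive. No test, model or causal claim is attached, and section 12.4 already refuses as-treated and per-protocol comparisons because of selection bias. All of this stands and limits the point to a reporting refinement. It does not supply the missing time order. Chart review and tracking could reveal an early start, but no visible text says what the table does with it. The chart review form and data abstraction sheet, which are not visible here, may hold more.

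Four stronger readings are tempting, and the documents do not support them:

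- **That 40% of starts (24/60, about 18 of 44) precede assessment.** This applies the latest scheduled call to everyone. Some patients are telephoned first, those never reached have no assessment, and section 12.2 expects most telephone outreach to be message reminders, not live contact. Also, the 24 excess starts are presumed to result from outreach and cannot precede it, although some could precede a reply.
- **That early starts must inflate initiation among responders.** If outreach stops at a start, the distortion runs the other way.
- **That these tables are the pilot's only evidence on barriers.** The Phase II focus groups and provider surveys also address barriers, and the preceding bullet tabulates need and barriers directly.
- **That a fixed landmark, say day 28, is needed.** It would discard 28/60 = 47% of follow-up and, with evenly spread starts, leave about 44 × 32/60 = 23 starts. It would also drop prompt starts that follow early outreach.

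**Conclusion.** The point holds as a minor one. As written, the last descriptive bullet mixes starts before and after the assessment or response by which patients are classified, and the resulting bias can go in either direction. Across the outreach arm, about 1-2 patients are misordered if only background starts can precede contact, and about 2-5 if all planned starts can. These ranges rest on 50% responding and on contact spread over 10 or 24 days from randomization. Faster contact makes them smaller; a delay before the first message or an early peak in starts makes them larger. A few patients can still produce a visible gap in a small table, more so once it is split by race/ethnicity. The intent-to-treat primary comparison, the sample size and the power are untouched.

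**What to change.** In section 12.4, amend the last descriptive bullet as follows:

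1. Confirm that the date of first outreach response or assessment is captured. The examples of shared data elements in section 33.5 name diagnosis, psychotherapy and fill dates but no outreach date; that list is only illustrative.
2. In the tables by PHQ-9, need and barriers, count only starts after that date and within 60 days of randomization, among patients still untreated at assessment.
3. List separately the patients already treated when first reached.
4. In the response versus no-response table, report starts before first contact or response separately, so that they are credited to neither group.

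The cost is a few lines of wording, a date comparison, one more date in the analysis file if it is not already there, and slightly fewer events in tables that are already small. Neither the intervention nor the sample size changes.

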**10.0**

## **General Section: Research Study Summary**

### **Study Abstract (S2)**

**10.1 \* What is your research question or hypothesis?**

Do outreach messages improve treatment initiation rates (within 60 days of outreach) for racial and ethnically diverse patients who have a new diagnosis of depression?

What type of outreach message is most effective (i.e., e-mail, direct message, telephone)?

What is the acceptability and effectiveness of different communication modalities (online messaging, mailed letters, telephone) among racial and ethnic minority populations?

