#### **Pilot Trial Design**

Each week, the computable EHR phenotype described above will be used to identify patients meeting criteria for failure to initiate depression treatment during the prior week. All eligible participants will be randomly assigned either to continued usual care (i.e. no contact from study staff) or to an outreach intervention described above. Engagement in care and recorded clinical outcomes over the subsequent 60 days will be assessed using health system records.

**Intervention Assignment** - All eligible patients will be randomly assigned (1:1 ratio) to either continued usual care or attempted outreach using a masked table of computer-generated random assignments. Randomization will be stratified by study site and use a permuted block design, with randomly varying block sizes of 4, 6, 8, 10 and 12.

**12.3 \* Provide a brief description about the quality management plan for the selection of study participants and integrity of the data. Specify the verification or audit process to ensure data and/or participants meet the study inclusion criteria. Additionally, describe the mechanism to ensure that study data is well secured and accurately entered. (e.g. two staff verification process to ensure entry criteria are met prior to using data or including a participant; safety reports; Data Safety Monitoring Board and/or screening checklists.)**

- All staff will be training in HIPAA privacy rules, human subjects protections, authorization of access by CIHR/HFHS IT, password protection, encryption, physical security, and separation of identifiers from data
- We plan to archive the deidentified data at the end of the study for the federally-mandated retention period or at least seven years, whichever is later.
- A Data Use Agreement will be executed between all sites prior to the transfer of any data. Data exchanged between the sites will contain the minimal information necessary and will be in the form of a limited data set.
- Data will be stored on password-protected encrypted devices and servers.

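### Section 12.4 gives the primary outcome two tests, ranks neither, and names no risk difference with an interval; the day-zero wording in 10.1 needs a consistency edit

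*Combined protocol and SAP*

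**What the plan says.** Section 12.4 sizes the trial on one comparison of two rates. It states "A sample size of 200 per group across both sites will afford 90% power", using a "chi-square statistic with 2-sided type 1 error of 5" per cent, "to detect an increase from 10% to 22% in those assigned to the outreach intervention". It expects that "only 2% will disenroll from participating health systems" within the follow-up window.

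For the analysis, the same section says "Unadjusted comparisons will use chi-square statistics to compare rates, and adjusted analyses will use logistic regression". The regression covariates are age group, earlier depression treatment, baseline PHQ-9 and site. The two secondary outcomes are to be analysed in the same way. No sentence ranks the two analyses, and none asks for an effect estimate with a confidence interval.

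Under Pilot Trial Design, "Randomization will be stratified by study site".

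On day zero, section 10.1 asks "Do outreach messages improve treatment initiation rates (within 60 days of outreach"), while section 12.4 says "The primary trial outcome will be initiation of formal depression treatment within 60 days of randomization".

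**The concern.** With two analyses of one primary outcome and no ranking, the conclusion can rest on whichever is significant. The 5% level belongs to a single test, so an either-test rule exceeds it. If the two disagree, the plan gives no way to settle the result.

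The estimate is also left open. The trial is sized on a difference in rates, but a logistic model reports a conditional odds ratio unless a further step is specified. The pilot is meant to inform a full-scale trial, for which a rate difference with its interval is the more useful product.

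The two other matters are smaller. The powered test leaves out the factor used to stratify randomization. The research question also starts the 60 days at an event that usual-care patients never have.

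**Working it through.** **1. The plan's own power.** Inputs from 12.4: p0 = 0.10, p1 = 0.22, n = 200 per group, two-sided 5%. The mean rate is 0.16.

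Power = Φ{[d − 1.96·√(2·p̄(1−p̄)/n)] / √([p0(1−p0) + p1(1−p1)]/n)}

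- √(2 × 0.16 × 0.84 / 200) = 0.03666, and × 1.96 = 0.07185
- √((0.0900 + 0.1716)/200) = 0.03617
- (0.12 − 0.07185)/0.03617 = 1.331, so power = 0.908
- With 2% loss, n = 196 per group and power = 0.903

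The stated 90% reproduces.

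**2. Ignoring the site strata.** Simulation of 8,000 trials per scenario, 100 patients per arm per site, non-prognostic covariates. Site-specific rates are assumed, because the documents give none. Rejection rate with no treatment effect:

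| Site rates | Chi-square | Site-stratified (Cochran-Mantel-Haenszel) |
|---|---|---|
| 10% / 10% | 4.8% | 4.8% |
| 5% / 15% | 4.6% | 5.0% |
| 2% / 18% | 4.1% | 5.2% |

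The Monte Carlo standard error near 5% is √(0.05 × 0.95/8000) = 0.24 points. The chi-square is valid and becomes slightly conservative as the sites diverge.

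**3. Two unranked tests.** Same simulation, chi-square against logistic regression with the plan's covariates. The assumed moderate log-odds effects are 0.5 per age-group step (three groups), 1.0 for earlier treatment (35% of patients) and 0.4 per 4 PHQ-9 points. Strong means double these. The effect scenarios use 10% against 22% at both sites, or usual-care rates of 5% and 15% with a common odds ratio of about 2.5.

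| Covariates | Either significant, no effect (equal; 5/15; 2/18) | Tests disagree, with effect (equal; 5/15) | Power, chi-square → logistic (equal; 5/15) |
|---|---|---|---|
| None | 5.1%; 5.1%; 5.3% | 1.3%; 1.7% | 91.7 → 91.2; 89.6 → 89.8 |
| Moderate | 6.2%; 5.8%; 5.3% | 4.0%; 4.6% | 90.5 → 92.0; 87.4 → 89.4 |
| Strong | 7.6%; 7.6%; 6.8% | 12.3%; 13.5% | 81.2 → 90.7; 78.7 → 89.3 |

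A second simulation (4,000–6,000 trials) gave either-test error of 5.3% with equal sites and of 5.9% and 6.1% with 5%/15% sites and moderate to strong covariates. Its power moved from 88.4% to 89.6% and from 87.6% to 90.6%, gains of 1.2 and 3.0 points.

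With no to moderate effects in the table, the gain runs from about −0.5 to +2.0 points. The larger gap in the strong row should not be read as a gain on the plan's scenario. Those runs hold the odds ratio fixed within covariate levels, so the overall rates move away from 10% and 22% and the chi-square loses power.

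**4. Scale of the estimate.** At the planned rates the difference is 12 points, with 95% interval 0.12 ± 1.96 × 0.03617, or 4.9 to 19.1 points. The corresponding odds ratio is (0.22/0.78)/(0.10/0.90) = 2.54. If covariates are prognostic, the regression's odds ratio is conditional on them and does not convert directly into the 12 points.

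**5. Day zero, place by place.** Section 10.1 counts from outreach. Section 12.4 counts from randomization, with no restriction to one arm, and its analysis paragraph refers back to that definition. Pilot Trial Design assigns both arms and then follows them for 60 days. Section 22.1 (Phase III) uses randomization but mentions only standard-care patients. Section 10.1 is the only text that departs from randomization.

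**The case against.** The power statement uses the chi-square, and the 5% level is attached to that test alone. A fair reader could take it as the intended primary analysis, and it already compares rates on the scale used for sizing. The inflation is small, depends on assumed covariate strength, and arises in a pilot. Much of this stands as to size. It does not close the gap: a test cited to justify the sample size is not thereby named primary, and the analysis paragraph lists the two side by side.

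Three stronger readings are tempting, and the documents do not support them.

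- **A different clock per arm.** From 10.1 a reader might infer that outreach patients are counted from outreach and usual care from randomization, which would favour outreach. No section plans this. The operative definition in 12.4 covers all participants, and usual care has no outreach date. Any figure for the bias would also need a lag from randomization to outreach, which the documents do not give.
- **Information from site and PHQ-9 thrown away.** The planned regression already includes both.
- **An invalid test or a wrong power figure.** The unstratified chi-square does not exceed 5% beyond simulation error, and the 90% reproduces.

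**Conclusion.** The point holds as a gap in specification with a modest, avoidable cost. The primary outcome has two unranked analyses and no stated estimate with an interval on the sizing scale. Letting either test decide puts type I error at about 5–6% with no to moderate covariate effects and at most about 7.6% in the scenarios tried. The tests would disagree in roughly 1–5% of trials under the planned effect, and in 12 to 13.5% if covariates are strong. Making the adjusted analysis primary costs essentially no power and gains up to about 3 points on the plan's scenario. Covariate effects, site rates and equal site sizes in the simulations are assumptions. That no analysis is ranked is read directly from the text.

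The site-strata matter is a reason for preferring the adjusted analysis and is not a separate defect. The day-zero matter is a wording inconsistency, since no biased analysis is planned.

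**What to change.** In 12.4, name one primary analysis, tested at two-sided 5%: the logistic regression already planned, with all four listed covariates (site, baseline PHQ-9, age group, earlier depression treatment). Report it as a standardised risk difference with 95% CI, obtained by averaging predicted risks under each assignment over all randomized patients with outcome data. Label the chi-square supportive, and say that the same ranking applies to the secondary outcomes.

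For consistency, change 10.1 to count the 60 days from randomization, and state in 22.1 that the same window applies to both arms.

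The cost is a few sentences and a standard marginal-standardisation step, with no change to sample size, covariates or data collection. The change should be made before outcome data are analysed.
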